Patient advocate

TBC

Sponsor

University of Cape Town

Funders

Society for the Advancement of Patient Blood Management

Table of Contents

1. LIST OF ABBREVIATIONS	4
2. SUMMARY	5
3. INTRODUCTION.....	6
4. STUDY OBJECTIVES.....	7
4.2 PRIMARY OBJECTIVE	7
4.2 SECONDARY OBJECTIVES	7
5. STUDY AIMS.....	7
5.2 PRIMARY OUTCOME MEASURE	7
5.2 SECONDARY OUTCOME MEASURES.....	7
6. METHODS	8
6.1 STUDY DESIGN	8
6.2 INCLUSION CRITERIA.....	8
6.3 EXCLUSION CRITERIA.....	8
6.4 SITE REQUIREMENTS	8
6.5 RESEARCH ETHICS AND INFORMED CONSENT	9
6.6 SUBJECT WITHDRAWAL.....	9
6.7 RECRUITMENT AND SCREENING	9
6.8 ENSURING ADEQUATE RESOURCES	10
6.9 CRITERIA FOR IRON DEFICIENCY	11
6.10 SUPPLEMENTAL IRON DOSING REGIMEN	11
6.11 EMPIRIC TREATMENT FOR WORMS.....	12
6.12 RESEARCH PROCEDURES, DATA COLLECTION AND COLLATION	13
6.13 DATASET.....	14
6.14 CASE RECORD FORMS.....	15
6.15 COLLECTION AND STORAGE OF BLOOD SAMPLES.....	15
6.16 MONITORING MEDICAL ADHERENCE	15
6.17 SAFETY REPORTING.....	16
5.10 EXPECTED BENEFITS TO INDIVIDUAL PARTICIPANTS AND POTENTIAL SOCIETAL BENEFITS ..	16
5.10 SAMPLE SIZE CALCULATION	17
5.10 POWER ANALYSES.....	17
5.11 STATISTICAL ANALYSIS.....	18
7. STUDY ORGANISATION AND MANAGEMENT	19
7.1 STUDY STEERING COMMITTEE	19
7.2 PATIENT ADVOCATE.....	19
7.3 LOCAL CO-ORDINATORS.....	19
7.4 TRAINING OF INVESTIGATORS	19
8. DATA MANAGEMENT AND OWNERSHIP.....	20
9. PUBLICATION PLAN.....	20
10. MANAGEMENT OF PREMATURE TERMINATION OF THE TRIAL.....	20
11. REFERENCES.....	21
10. APPENDICES	24

1. List of abbreviations

DHb	Delta haemoglobin (pre-treatment haemoglobin – post-treatment haemoglobin)
Hb	Haemoglobin
IDA	Iron deficiency anaemia
SAPSOS	South African Paediatric Surgical Outcomes Study

2. Summary

Short title	SAPSOS-2: Pilot Study
Methodology	Prospective national multi-centre interventional study
Research sites	Hospitals undertaking paediatric surgery in South Africa
Objective	To evaluate the efficacy of oral iron supplementation in children diagnosed with preoperative iron-deficiency anaemia undergoing noncardiac surgery.
Primary outcome	The delta Hb (DHb) (pre-intervention Hb –post-intervention Hb)
Number of patients	1110 patients
Inclusion criteria	Paediatric patients aged >6 months and <16 years admitted to participating hospitals undergoing elective non-cardiac surgery Anaemia as per WHO criteria ¹
Exclusion criteria	Patient or parent refusal Surgery planned in not less than 4 weeks from surgical outpatient visit Known history of acquired iron overload, family history of haemochromatosis or thalassemia Known reason for anaemia (e.g. untreated vitamin B ₁₂ or folate deficiency or haemoglobinopathy) Treatment with oral iron, erythropoietin, IV iron therapy or blood transfusion in the previous 12 weeks Known hypersensitivity to oral iron or other contraindication to oral iron Temperature > 38.0 °C or receiving non-prophylactic antibiotics
Statistical analysis	The primary outcome measure is comparison of pre-intervention and post-intervention haemoglobin
Proposed start date	08 February 2023
Proposed end date	26 July 2024
Trial duration	Recruitment in outpatient clinic and follow-up until day of surgery

3. Introduction

Studies in both paediatric and adult patients have shown an association between preoperative anaemia and increased postoperative morbidity and mortality, and transfusion rates²⁻⁷. The incidence of preoperative anaemia in the secondary analysis of the SAPSOS cohort of children who underwent noncardiac surgery was 46.2%⁴. Iron deficiency anaemia (IDA) has been shown to represent up to 30% of preoperative anaemia in adults⁸. Iron deficiency and IDA are of even greater concern in children, because of the negative impact it may have on cognitive performance⁹.

A recent Cochrane review on the role of preoperative iron in reducing perioperative blood transfusion in adult patients found no significant reduction in the administration of allogeneic blood transfusion in patients who had received preoperative iron compared with those who did not¹⁰. These findings were supported by the Preoperative intravenous iron to treat anaemia before major abdominal surgery (PREVENTT) trial which found no difference in blood transfusion or death between the patients who did and did not receive intravenous iron¹¹. However, these findings have generated much discussion in the literature and concerns have been raised about the clinical application of this study. The mean Hb difference between the two groups post intervention (0.47g.dL⁻¹) highlights the need for greater understanding of the impact of an intervention on the absolute or relative increase in Hb when designing trials looking at the impact of iron treatment on perioperative outcomes. Dosing regimens of preoperative oral iron varies widely between studies further complicating the ability to draw conclusions of the role of oral iron in the treatment of preoperative anaemia¹²⁻¹⁶.

In contrast with the findings of the Cochrane review and the PREVENTT trial, a meta-analysis of patient blood management programme (PBM) studies, many of which include preoperative iron treatment as a component, found that there was a reduction in exposure to red cell transfusions¹⁷. Although, the meta-analysis also found the implementation of PBM was not associated with a reduction on in-hospital mortality or 30-day mortality, there was no additive benefit from multiple interventions and no trial showed that PBM were cost-effective.

Not included in this meta-analysis were recently published studies on the implementation of preoperative anaemia screening clinics in adults in elective colorectal surgery and major surgery which demonstrated reductions in red cell transfusions^{18,19}, length of stay^{18,19}, and net costs¹⁸ in patients with IDA who were treated with preoperative intravenous iron. Similarly, a large study from Western Australia reported significant reductions in cost associated with the use of blood products, and improved patient outcomes, after implementation of a PBM²⁰.

Studies investigating the impact of increasing preoperative haemoglobin on perioperative outcomes in children are primarily focused on blood loss and blood transfusion rates in surgery in which significant bleeding and frequent blood transfusion are anticipated and most children in these studies received preoperative erythropoietin²¹⁻²⁷. The impact of preoperative oral iron as a stand-alone intervention to increases preoperative Hb are limited to 2 studies^{28,29}. A single retrospective study has reported on the impact of the introduction of preoperative oral iron without EPO in children undergoing spinal surgery²⁸. They found a significant difference in intraoperative transfusion rates in patients who received a longer duration of preoperative oral iron therapy. The major limitation of the study was a lack of preintervention Hb, precluding the ability to assess the effect of iron supplementation on delta Hb.

A subsequent study reviewing the impact of preoperative oral iron in paediatric cardiac patients found that iron supplementation resulted in an increase in preoperative haemoglobin levels which was associated with reduced red blood cell transfusion volumes²⁹.

Given the high incidence of preoperative anaemia in children having surgery in South Africa in the public sector and its association with poorer postoperative outcomes, it is important to assess the feasibility of a pragmatic intervention to treat preoperative anaemia in the context of a resource-constrained setting. Although intravenous iron in combination with EPO may be more effective and have fewer side effects, oral iron is relatively inexpensive and widely available in South Africa. Regular deworming may also play an important role in the treatment of preoperative anaemia and has been shown to be an effective intervention to increase baseline Hb in school age children from low- and middle- income countries³⁰.

We hypothesise that the implementation of preoperative anaemia screening and treatment of anaemic patients with a minimum of 6 weeks supplementation with oral iron will have a clinically significant effect on increasing the haemoglobin in patients with preoperative IDA.

4. Study objectives

4.2 Primary objective

To evaluate the efficacy of oral iron supplementation in children diagnosed with preoperative IDA undergoing noncardiac surgery.

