5.2 Primary outcome measure

DHb (pre-intervention Hb – post-intervention Hb)

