6.1 Study design

Prospective interventional quasi-experimental pre-post study across multiple hospitals in South Africa. Patients will be screened for trial eligibility at a normal routine outpatient clinic visit. Those patients with a screening Hb meeting the criteria for anaemia according to the WHO definition³⁰ and able to receive the oral iron for a minimum of 6 weeks prior to their planned operation, will be eligible for inclusion.

The formal laboratory blood test results will be reviewed within 48-76 hours by the research nurse to diagnose those patients who meet the pre-defined criteria for IDA. Parents & legal guardians will be contacted via telephone by the research nurse to inform them about their child's results and to instruct them to either discontinue or continue taking the oral iron supplementation dependent on whether the results meet the pre-defined criteria for iron-deficiency anaemia.

Prior to inclusion, freely given written informed consent must be obtained from all parents or legal guardians and assent from patients where appropriate.

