6.12 Research procedures, data collection and collation

At recruitment phase

Eligible patients will be screened for anaemia with a finger-prick bedside Hemacue test at outpatient clinic. If the patient meets the WHO criteria for anaemia EMLA cream will be applied to potential sites for venepuncture and the patient will then be sent to the pathology laboratory for venepuncture with a request form for tests that will include laboratory full blood count (FBC), ferritin, transferrin saturation (TSAT), C-reactive protein (CRP), and reticulocyte Hb content. Patients who have not been dewormed within the last 6 months will be treated with mebendazole or albendazole as per the South African guidelines³³.

The patients age, weight, height, co-morbidities, ASA physical status, planned surgical procedure, planned date of surgery, severity of surgery, and type of surgery will be recorded. They will also be informed that they will be contacted telephonically once a week by the research assistant to enquire about compliance with the medication and enquire about any side-effects with the medication. The telephonic contact details will be confirmed by the research nurse and documented on the paper Outpatient CRF.

At home

The laboratory blood test results will be reviewed within 48 hours to diagnose those patients who meet the criteria for IDA. Any patients who do not meet the criteria will be contacted via telephone by the research nurse to instruct them to stop taking the iron supplementation and to bring the remaining iron supplementation with them to their next hospital visit. These patient folders and results for those patients not meeting the criteria for IDA will be reviewed by the appropriate surgical team to decide on appropriate ongoing management and further investigations which will be individualised to the patient.

For those patients meeting the criteria for IDA and continuing the oral iron supplementation, the parent or legal guardian will be contacted weekly to complete a short telephonic survey on compliance with the medication, side-effects, and to answer any questions or concerns they may have.

At time of Surgery

Repeat laboratory FBC at time of routine preoperative bloods if part of standard care.

Repeat ferritin, CRP, TSAT ± FBC whilst under anaesthesia prior to start of surgery.

Data collection

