6.13 Dataset

A realistic data set will be fundamental to the success of the investigation. This dataset will include the following:

All patients:

- Age (continuous, numerical)
- Sex (categorical, nominal)
- Weight (continuous, numerical)
- Height (continuous, numerical)
- Co-morbidities (categorical, nominal)
- Chronic medication (categorical, nominal)
- ASA Physical Status (categorical, ordinal)
- Severity of surgery (categorical, nominal)
- Type of surgery (categorical, nominal)
- Hemacue Hb

All anaemic patients

- Pre-intervention Hb (continuous, numerical)

- Pre-intervention MCV (continuous, numerical)
- Pre-intervention ferritin (continuous, numerical)
- Pre-intervention TSAT (continuous, numerical)
- Pre-intervention CRP (continuous, numerical)
- Pre-intervention reticulocyte Hb content (continuous, numerical)
- Syrup or tablet prescribed (categorical, nominal)
- Actual dose of elemental iron prescribed ($\text{mg}^{-1} \cdot \text{kg}^{-1} \cdot \text{day}^{-1}$)

All patients with IDA

- Post-intervention Hb (continuous, numerical)
- Post-intervention MCV (continuous, numerical)
- Post-intervention ferritin (continuous, numerical)
- Post-intervention TSAT (continuous, numerical)
- Post-intervention CRP (continuous, numerical)
- Post-intervention reticulocyte Hb content (continuous, numerical)
- Days of oral iron treatment (continuous, numerical)

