5.11 Statistical analysis

Categorical variables will be reported as number and percentage. All patient and surgical characteristics will be compared between children with and without anaemia and comparing children with IDA versus anaemia of other cause using Pearson's chi-squared or Fisher's exact tests as appropriate. These will include age groups, sex, type of surgery (general, orthopaedic, ENT, plastics, other), severity of surgery as per SAPSOS definitions (mild, moderate, severe), severity of anaemia as per WHO definitions (mild, moderate, severe).

Normal distribution of continuous variables will be determined by Shapiro-Wilk testing and summarised appropriately as means \pm standard deviation or as medians \pm interquartile range (IQR). All patient and surgical characteristics will be assessed with parametric testing (Student's t-test) for normally distributed data, and nonparametric testing (Mann-Whitney U test or Kruskal-Wallis test) for non-normally distributed data. These data will include pre-intervention Hb, post-intervention Hb, and duration of oral iron treatment (days).

Pre- and post-intervention Hb for the patient with IDA will be assessed by a paired t-test if data are normally distributed, and if data are not normally distributed then the data will be analyse using Wilcoxon ranked sum test.

Is there a statistically significant difference in pre and post intervention Hb in the IDA patients after adjusting for baseline haemoglobin?

The proposal is to use a mixed effect regression model. The final model will depend on the distribution of the outcome variable (post-intervention Hb). If the outcome is normally distributed, a linear mixed effect model will be used. If the outcome is not normally distributed, different approaches can be used depending on how skewed the outcome is e.g. Generalised Linear Mixed Effect Model

7. Study organisation and management

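### Children enter on a low Hb and the treated IDA group is tested against no change, so a significant rise in Hb does not by itself show that iron works.

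*Combined protocol and SAP*

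**What the plan says.** Section 6.1 of the combined protocol and SAP describes a "Prospective interventional quasi-experimental pre-post study across multiple hospitals in South Africa". Entry depends on a low reading: "Those patients with a screening Hb meeting the criteria for anaemia according to the WHO definition" are eligible if they can also take iron for long enough before surgery. Section 6.12 names the instrument: "Eligible patients will be screened for anaemia with a finger-prick bedside Hemacue test at outpatient clinic". Children who screen positive go on to laboratory venepuncture from that clinic attendance, and 6.13 lists the finger-prick Hb and the pre-intervention Hb as separate items.

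The primary outcome (5.2) is "DHb (pre-intervention Hb – post-intervention Hb"), so a rise in Hb appears as a negative DHb. Section 5.11 sets the test: "Pre- and post-intervention Hb for the patient with IDA will be assessed by a paired t-test if data are normally distributed", with a rank test otherwise. A mixed model adjusting for baseline Hb follows, also in IDA children only. The objective in 4.2 is nevertheless causal: "To evaluate the efficacy of oral iron supplementation in children diagnosed with preoperative IDA undergoing noncardiac surgery". The Summary repeats it, and the hypothesis in section 3 speaks of an effect on Hb.

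Anaemic children without IDA are told to stop iron (6.12). Section 6.13 lists post-intervention Hb only under "All patients with IDA". Children not dewormed in the last six months receive deworming medication (6.11, 6.12), which section 3 says raises Hb in school-age children. Regression to the mean is not mentioned.

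**The concern.** A child selected on one low reading is, on average, nearer to his or her usual level the next time. If part of the low value is a temporary state on the clinic day, such as hydration, recent illness or posture, it depresses both the finger-prick reading and the laboratory sample taken soon after. That part is gone by the day of surgery, and Hb rises without any treatment effect. The paired test has no way to tell this from a response to iron, because zero change is not what is expected of untreated children chosen in this way.

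Adjusting for baseline Hb does not solve it. The model contains only treated IDA children, so it has no untreated reference from which to estimate the expected rise. A larger sample does not help either: the bias stays the same while the standard error shrinks. At stake is whether the primary result can carry the word efficacy.

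**Working it through.** **1. The plan's own figures.** Solving the paired t-test (noncentral t, 80% power, two-sided 0.05) for the standardised effect gives 0.2123 at 176 pairs (stated 0.2123609) and 0.488, 0.392, 0.340 and 0.302 at 35, 53, 70 and 88 pairs (stated about 0.5, 0.4, 0.34 and 0.3). The arithmetic is sound, and it confirms that the reference value is zero change. At the 44 IDA children in the 6.7 site table the same formula gives 0.432.

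**2. Inputs.** From the documents: 46.2% below the cut-off (5.10 Sample size), 44 pairs (6.7), two-sided 5% (5.10 Power analyses). Assumed, because the documents do not give them:
- laboratory Hb SD 1.5 g/dL
- visit-to-visit correlation ρ from 0.80 to 0.95
- finger-prick error SD e from 0 to 0.8 g/dL
- share q of the within-child variance that is common to the two same-day samples
- one cut-off, and IDA children treated as a random sample of anaemic children

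**3. Formula, with no iron effect.** Within-child variance w = (1−ρ)·SD². SD of the finger-prick reading s = √(ρ·SD² + q·w + e²). For selection below the 46.2% point, a = −0.095 and λ = φ(a)/Φ(a) = 0.860.

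Expected rise = q·w·λ/s.

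The variance of the paired difference is 2w − c²(1−v), with c = q·w/s and v = 1 − aλ − λ² = 0.343.

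**4. Worked ends of the range, all variation shared (q = 1).**
- ρ = 0.80, e = 0: w = 0.2 × 2.25 = 0.45, s = 1.50. Rise = 0.45 × 0.860/1.50 = 0.26 g/dL. SD of the difference 0.917, standardised effect 0.28.
- ρ = 0.95, e = 0.8: w = 0.1125, s = √(2.25 + 0.64) = 1.70. Rise = 0.1125 × 0.860/1.70 = 0.06 g/dL. SD of the difference 0.471, standardised effect 0.12.

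**5. Results at 44 pairs** (noncentral t, checked by simulation; nominal chance of a significant rise is 2.5%).

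| Share q | Spurious rise, g/dL | False significant rise |
|---|---|---|
| all | 0.06 to 0.26 | 12% to 44% |
| half | 0.03 to 0.14 | 6% to 15% |
| a quarter | 0.01 to 0.07 | 4% to 7% |
| none | 0 | 2.5% |

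**6. Why the choice of baseline matters.** If the finger-prick value itself were used as baseline, device error would regress too. The rise becomes (s² − ρ·SD²)·λ/s. At ρ = 0.80, e = 0.8 and q = 1 this is (2.89 − 1.80) × 0.860/1.70 = 0.55 g/dL, against 0.45 × 0.860/1.70 = 0.23 g/dL with the laboratory baseline.

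**7. Scale.** Section 3 discusses a 0.47 g/dL between-group difference from an adult intravenous iron trial. The fully shared range is 0.06/0.47 = 13% to 0.26/0.47 = 55% of that.

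**The case against.** The strongest reply is that the plan already limits the damage. Selection uses the finger-prick device, while 6.13 keeps a separate laboratory baseline, so device error should not enter DHb. If the two samples shared no temporary variation there would be no inflation at all. This stands, and it is why the size must be shown across q. Complete absence of sharing is unlikely for two samples from one attendance.

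Second, the test is run in IDA children, who are selected again on ferritin or transferrin saturation. If their usual Hb is truly lower, fewer fall below the cut-off by chance. As an illustration, take 12% of screened children with a mean 1.5 g/dL lower, e = 0.8 and q = 1. The cut-off then lies 0.69 SD above their mean, λ falls to 0.418, and the rise is 0.1125 × 0.418/1.70 = 0.03 to 0.45 × 0.418/1.70 = 0.11 g/dL, with a false significant rise in about 6% to 12% of trials. This also stands.

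Third, this is a named pilot that openly calls itself quasi-experimental. That lowers the severity, but it does not turn a pre-post test into evidence of efficacy.

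Three stronger readings are tempting and are not supported:
- *Any positive result could be wholly regression to the mean.* The largest spurious rise in the step 5 range is 0.26 g/dL, and the hypothesis concerns a clinically significant effect. The threat is to a small rise, although the plan does not define how large a clinically significant rise is.
- *Section 5.11 already plans an IDA versus non-IDA comparison of post-intervention Hb that 6.13 makes impossible.* The sentence "These data will include pre-intervention Hb, post-intervention Hb, and duration of oral iron treatment (days") names no groups, and it includes treatment duration, which 6.13 also lists only for IDA children. It can equally describe the IDA cohort.
- *A control arm was considered and set aside.* The documents record no such decision.

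**Conclusion.** The concern holds in a limited form. Selection on a low Hb, a same-attendance baseline, one treated group and a test against zero are all in the current text, so a significant DHb cannot by itself establish efficacy. Deworming given with the iron points the same way.

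The size is uncertain. It rests on an assumed SD, correlation and device error, and above all on the share of same-day variation common to the two samples. A reader might take 12% to 44% as this trial's false-positive rate. It is the upper case, with everything shared. Across the shares examined the range runs from 2.5% to 44%, and the second selection on iron markers probably lowers it. Severity: should be fixed, because it changes what the primary result can be said to show and the correction is cheap.

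**What to change.** 1. In 4.2, the Summary objective and the section 3 hypothesis, replace the efficacy wording with *change in Hb during preoperative oral iron (with deworming where given)*, and state that efficacy will not be concluded from the paired test alone.
2. In 5.2 and 6.13, state that the pre-intervention Hb in DHb is the laboratory FBC, never the finger-prick value that selected the child.
3. In 5.11, report mean DHb with a 95% confidence interval. Add a sensitivity analysis that compares it with the rise expected from regression to the mean, over stated ranges of the visit-to-visit correlation and of the share of variation common to the two same-day samples. The finger-prick Hb recorded for all screened children can supply the SD, after device error has been removed from it.
4. Optionally, where a routine preoperative FBC exists for anaemic children without IDA, abstract it and report their DHb descriptively. They are an imperfect reference: they take iron briefly, are managed individually and may have a different Hb distribution. Their DHb should not be subtracted as though it isolated the effect of iron.

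The cost is wording and a short extra analysis, with no new blood samples. Item 4 needs a small addition to 6.13 and to the Surgical Admission CRF, which now covers only the IDA cohort. The downside is a weaker headline claim.
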